3.6.2. Deaths, Serious Adverse Events and Other Significant Adverse Events

3.6.2.1. Adverse events of special interest

Adverse events of special interest include the following, with additional PTs to be determined at time of database lock;

Hypersensitivity and Anaphylactic Events

The subset of adverse events with a MedDRA coded SOC of Immune system disorders and PTs of Hypersensitivity, Anaphylactic reaction and Anaphylactoid reaction.

Events Associated with C-SSRS

The subset of adverse events with a MedDRA coded SOC of Psychiatric disorders and PTs of Suicidal behavior, Suicidal ideation, Suicidal attempt and Self injurious behavior.

Cardiovascular Events

The subset of adverse events with

- a MedDRA coded SOC of Cardiac disorders and PTs of Atrial fibrillation, Bradycardia, chest pressure, Palpitations, Sinus bradycardia, Sinus tachycardia and Tachycardia, or
- a MedDRA coded SOC of Investigations and PTs of Blood pressure increase, Blood pressure systolic increase, Elevated blood pressure, Heart rate increased, Heart rate decreased, Heart rate irregular, Electrocardiogram abnormal, Electrocardiogram Q wave abnormal, Electrocardiogram QT interval abnormal, and Electrocardiogram QT prolonged, or
- a MedDRA coded SOC of Nervous system disorders and PTs of Seizure and Syncope, or
- a MedDRA coded SOC of Vascular disorders and PTs of Flushing, Hot flush, Hypertension, Hypotension and Ischemia.

Hepatic Events

A subset of adverse events with a MedDRA coded SOC of Investigations and PTs of Alanine aminotransferase increased, Aspartate aminotransferase increased, Bilirubin increase, Hepatic enzyme increased, Liver function test abnormal, and Transaminases increased.

Events Associated with Study Drug Infusion

A subset of adverse events within one week of dosing with

- a MedDRA coded SOC of Skin and subcutaneous tissue disorders and PTs of Dermatitis bullous, Pruritus, Pruritus generalized, Rash, Rash macular, Rash macular-papular, Rash papular, Rash pruritic and Urticaria.
- a MedDRA coded SOC of General disorders and administration site conditions and PTs of Infusion site erythema, Infusion site extravasation, Infusion site pain, Infusion site paresthesia, Infusion site pruritus, Infusion site rash, Infusion site reaction, and Infusion site swelling.

Adverse Event of Interest Analysis

The adverse events of special interest will be summarized and listed in the following categories:

- AESIs by system organ class and preferred term.
- AESIs by system organ class, preferred term, and maximum severity.
- AESIs by system organ class, preferred term, and relationship to study drug.
- AESIs that lead to infusion interruption by system organ and preferred term.
- AESIs with action taken of study drug discontinuation by system organ class and preferred term
- AESIs assessed as serious by system organ class and preferred term.

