5.4. Risks and Benefits

ALD403 may prevent migraine from occurring in patients treated in this trial. No specific toxicities or adverse effects related to the blockade of CGRP by ALD403 have been identified in either the nonclinical toxicology program or the clinical trials with ALD403 that have been completed to date.

There may be unknown adverse effects and unforeseeable risks associated with study drug administration or unexpected interactions with another drug that have not yet been identified.

As with all protein therapeutics, there is a risk of a serious allergic reaction. In completed ALD403 trials conducted to date, no serious allergic reactions have been observed with the administration of ALD403 in humans.

In the completed ALD403 clinical trials with headache patients, the most common observed adverse events (>5%) with receiving ALD403 or placebo included upper respiratory tract infection, back pain, dizziness, arthralgia, urinary tract infection, and headache. The majority of these adverse events were categorized as mild to moderate.

Long term data with ALD403 is limited.

- Healthy volunteer trials have included limited dosing, short duration of follow up and have not include long term follow-up.
- Trials in migraine patients have also included limiting dosing. These trials are currently ongoing and no new significant findings have been noted during the follow-up period to date.

The safety findings to date indicate that ALD403 Injection is well tolerated, and demonstrates a favorable benefit-risk profile based on review of nonclinical, clinical, and scientific literature data.

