11.2. Management of Reactions to ALD403

There are no specific antidotes to ALD403.

Each medical emergency should be treated appropriately by the Investigator using proper standard of care, according to their typical clinical practice and local guidelines for that emergency condition. Emergency equipment and medication for the treatment of these potential adverse events must be available for immediate use.

Should a medical condition arise that the Investigator believes is related to the Investigational Product, clinical judgment should be used to provide the appropriate response including the consideration of discontinuation of Investigational Product. Any events believed to be potential allergic reactions should be discussed with the Medical Monitor.

If a subject experiences a potential systemic allergic reaction, as assessed by the Investigator, the site will collect additional blood specimens using the immune response lab kit, per the laboratory manual, at the time of the event and again at the next scheduled visit. This assessment includes serum histamine, serum tryptase, immunoglobulin E, and complement components. Subjects

who have experienced a potential significant allergic reaction after administration of Investigational Product should not receive subsequent doses.

Whether maintained in a “formal crash cart” or separately, the following is a requirement at the site:

- CPR certification by site staff performing study assessments
- Automated external defibrillator (AED)
- Emergency medications including antihistamines, bronchodilators, IV saline, corticosteroids, acetaminophen, and epinephrine

The AED and emergency medication should be immediately available on an Investigational product infusion day.

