3.6.3. Clinical Laboratory Evaluations

Summary statistics for actual values and for changes from baseline will be tabulated for clinical laboratory results by scheduled visit. Subjects with clinical laboratory values outside of the normal reference range at any post-baseline assessment will be summarized. Shifts from baseline clinical laboratory values based upon the normal range and will be tabulated. Subjects developing an antibody response will be listed. A listing of the Immune response laboratory results will be produced.

Plots of average clinical laboratory parameters will be presented over time.

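### The hypersensitivity AESI names three preferred terms, leaves further terms to database lock without a rule, and has no way to join allergic signs within a subject, so its count may be too low

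*SAP*

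**What the plan says.** Protocol 5.4 names the risk: "As with all protein therapeutics, there is a risk of a serious allergic reaction". It adds that no serious allergic reaction was seen in the completed trials.

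SAP 3.6.2.1 opens with "Adverse events of special interest include the following, with additional PTs to be determined at time of database lock". The section then spreads possible signs of allergy over three categories:

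- **Hypersensitivity:** "The subset of adverse events with a MedDRA coded SOC of Immune system disorders and PTs of Hypersensitivity, Anaphylactic reaction and Anaphylactoid reaction". No time window is stated.
- **Study drug infusion:** "A subset of adverse events within one week of dosing with" skin terms, namely "Dermatitis bullous, Pruritus, Pruritus generalized, Rash, Rash macular, Rash macular-papular, Rash papular, Rash pruritic and Urticaria", or infusion-site terms.
- **Cardiovascular:** among others "a MedDRA coded SOC of Vascular disorders and PTs of Flushing, Hot flush, Hypertension, Hypotension and Ischemia", plus syncope under the nervous system class. No time window is stated.

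The planned AESI outputs are by system organ class (SOC) and PT.

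Protocol 11.2 has the investigator identify the cases clinically: "If a subject experiences a potential systemic allergic reaction, as assessed by the Investigator, the site will collect additional blood specimens". These are tested for histamine, tryptase, immunoglobulin E and complement. For these results SAP 3.6.3 says: "A listing of the Immune response laboratory results will be produced".

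**The concern.** An AESI category should let a reader see, per arm, how many subjects had the reaction of interest. Here the answer depends on how a site words the event. A reaction recorded as hypersensitivity is counted. The same reaction recorded as urticaria and hypotension falls into two other categories and not into this one. Urticaria that starts on Day 10 is in no named AESI category. Subjects whom the investigator judged to have a potential systemic allergic reaction appear in a laboratory listing but are not counted as a group.

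The open term list adds a second problem. Terms can be added late, no selection rule is given, and the SAP does not say which lock is meant. If it is a lock after Week 32, some sponsor staff may already know treatment assignments when terms are chosen.

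Allergic reaction is a risk the protocol itself singles out. Protocol 5.3.1 also reports one fatal anaphylactoid-like event in a monkey after repeated dosing, attributed to anti-drug antibodies. A clear per-arm count in a repeat-dose trial is worth having.

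**Working it through.** The documents give no rate of allergic reactions and no figure for this category, so there is nothing to reproduce. The check is mainly textual.

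**Where each recorded event goes under SAP 3.6.2.1 as written, with no terms added**

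| Recorded as | Within one week of dosing | Later |
|---|---|---|
| Hypersensitivity, anaphylactic or anaphylactoid reaction | Hypersensitivity | Hypersensitivity |
| Urticaria, rash, pruritus (listed skin terms) | Infusion | No named AESI category |
| Hypotension, flushing, syncope | Cardiovascular | Cardiovascular |
| Urticaria plus hypotension, same subject | Infusion and cardiovascular, not joined | Cardiovascular only |
| Investigator-assessed reaction with kit drawn (Protocol 11.2) | By coded term only; kit results listed | By coded term only; kit results listed |

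Only the skin and infusion-site terms leave the AESI output after a week.

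**Length of the window.** Doses are on Days 0 and 84, and follow-up ends on Day 224 (SAP 1.2). Two 7-day windows cover 2 × 7 / 224 = 6.25% of post-dose days. If both end days count, it is 2 × 8 / 225 = 7.1%. This is a share of days, not of reactions: infusion reactions cluster near dosing, so the share of events missed could be far smaller than 93%.

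**Illustration of the possible size (rates and coding shares assumed).** The two active arms have 2 × 350 = 700 subjects (SAP 1.5). Expected count in the three-term category = 700 × true rate × share coded to the three terms. The chance of seeing at least 3 is the binomial tail.

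| True rate | 100% coded to the three terms | 75% | 50% | 25% |
|---|---|---|---|---|
| 0.5% | 3.5 (68%) | 2.6 (49%) | 1.75 (26%) | 0.9 (6%) |
| 1% | 7.0 (97%) | 5.25 (90%) | 3.5 (68%) | 1.75 (26%) |
| 2% | 14.0 (>99%) | 10.5 (>99%) | 7.0 (97%) | 3.5 (68%) |

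Each cell shows the expected subjects, with the chance of at least 3 in brackets.

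Within one arm of 350, suppose 5 subjects react and 2 are coded to the three terms. The category shows 2/350 = 0.6% (exact two-sided 95% upper limit 2.0%) instead of 5/350 = 1.4% (upper limit 3.3%). If none is so coded, it shows 0/350 (upper limit 1.0%).

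**Timing of added terms.** SAP 1.4 unblinds limited sponsor representatives once the last subject completes Week 12. Follow-up runs to Week 32. Terms chosen at a final lock would come after that unblinding; terms chosen at a lock before it would be chosen blind. The SAP does not say which applies.

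**The case against.** The case for leaving the plan alone has real substance.

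- **The list is open.** Urticaria could be added to the hypersensitivity category at lock, and since that category has no window, the one-week limit would no longer matter for it. This stands. But adding terms does not join signs within a subject or count the investigator-assessed cases, and it leaves the definition unfixed while some staff may be unblinded.
- **Sites are steered to a diagnosis.** Protocol 11.1.3 asks investigators to group signs of one diagnosis under one term where they can, and Protocol 11.2 sends suspected allergic reactions to the Medical Monitor. Recording by separate signs is therefore not the default. This lowers the likely shortfall but does not remove it, because the instruction is conditional and the SAP's own lists provide for sign-level terms.
- **Nothing disappears.** SAP 3.6.1 tabulates all treatment-emergent events by SOC and PT with no window and lists every event by subject; SAP 3.6.2.2 lists and summarises all serious events. This stands in full. A reader might infer that allergic reactions go unreported, or that hypotension and flushing are lost after a week. The documents support neither. What is missing is one subject-level count, which PT tables cannot supply.
- **Benefit-risk does not rest on this count.** Protocol 5.4 bases its statement on nonclinical, clinical and literature review, and its remark on serious reactions concerns completed trials. This stands.
- **A broad category is less specific.** Isolated rash weeks after dosing is often not allergic. This is fair, and is why the narrow row should be kept.

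**Conclusion.** The point holds as a limited one. As written, SAP 3.6.2.1 yields no per-arm count of subjects with an allergic reaction, however recorded. Its hypersensitivity count may be too low, by an amount that depends on a reaction rate and a coding split the documents do not give. The figures above show only what the shortfall would be under assumed values; with every reaction coded to the three terms it is zero.

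The open term list is a separate weakness: it has neither a selection rule nor a stated date relative to unblinding. A reader might infer that terms would be picked to suit the result. Nothing in the documents suggests that; the SAP simply does not exclude knowledge of treatment when the terms are chosen.

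This is a cheap improvement to safety reporting. It does not affect the efficacy analyses.

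**What to change.** In SAP 3.6.2.1, settle the term list before any unblinding and define a subject-level any-hypersensitivity AESI, met by any of:

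1. one of the three listed PTs;
2. a listed skin PT at any time after dosing, shown by time since the last infusion (same day, Days 1-7, after Day 7);
3. a prespecified combination of signs across categories, for example a listed skin PT with hypotension, flushing or syncope close in time, with the interval stated, shown as its own row;
4. an investigator-assessed potential systemic allergic reaction with an immune response kit drawn under Protocol 11.2.

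Report the incidence per arm with a confidence interval, and keep the three-term count as a separate narrow row.

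The cost is SAP wording and one table from data already collected; no clinical procedure changes. The downside is that the broad row takes in some non-allergic rash and pruritus in all arms. Comparison with placebo and the narrow row allow for that.

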3.6.2.2. Serious Adverse Events

All SAEs will be listed and summarized in a similar manner to TEAEs.

3.6.2.3. Deaths

A listing of deaths will be presented.

3.6.3. Clinical Laboratory Evaluations

Summary statistics for actual values and for changes from baseline will be tabulated for clinical laboratory results by scheduled visit. Subjects with clinical laboratory values outside of the normal reference range at any post-baseline assessment will be summarized. Shifts from baseline clinical laboratory values based upon the normal range and will be tabulated. Subjects developing an antibody response will be listed. A listing of the Immune response laboratory results will be produced.

Plots of average clinical laboratory parameters will be presented over time.

3.6.4. Vital Signs, Physical Findings and Other Observations Related to Safety

3.6.4.1. Vital Signs

The observed data at baseline and change from baseline for each measurement day will be summarized with descriptive statistics. A plot of average vital sign parameters will be presented over time.

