11.1.2. Assessment of Adverse Events

The Investigator is required to monitor the occurrence of adverse events for each subject from the time of informed consent through the course of the clinical trial. Adverse events may be reported by the subject, reported by a caregiver, or reported by the investigative site through Investigator site personnel open-ended questioning, through physical examination, laboratory test, documentation in medical records, or by other means. Adverse events include:

- Any new undesirable medical experience or an unfavorable and unintended change of an existing condition that occurs during or after treatment, whether or not considered related to the Investigational Product.
- Any abnormal assessment or laboratory findings considered by the Investigator to be clinically significant. Clinically significant findings include but are not limited to those that lead to discontinuation or interruption of study treatment, require therapeutic intervention, or require a change in subject management.

A new or worsening of a pre-existing or chronic condition is considered an adverse event and must be reported as such. Medical conditions, which existed prior to the time of informed consent into the clinical trial, will not be considered an adverse event unless the condition worsens. Unchanged, chronic, non-worsening or pre-existing conditions from the time of informed consent are not adverse events and should not be recorded on the AE eCRF.

Pre-existing medical conditions of clinical significance must be included in the subject's medical history and recorded on the medical history eCRF page.

Each event recorded on the AE eCRF is required to be assessed by the Investigator with regard to the following; seriousness, severity, and relationship to Investigational Product, as outlined below.

Seriousness

An adverse event or suspected adverse event is considered serious if in the view of either the Investigator or Sponsor, it results in;

- Death
- Is life-threatening (this means that the subject is at risk of death at the time of the event; it does not mean that the event hypothetically might have caused death if it were more severe)
- Inpatient hospitalization or prolonged existing hospitalization
- A persistent or significant incapacity or substantial disruption of the ability to conduct normal life functions.
- Congenital anomaly/ birth defect

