13.4. Statistical Methods

Continuous variables will be summarized with mean, median, standard deviation, minimum, and maximum. Categorical variables will be summarized with frequency and percentage.

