3. STATISTICAL SUMMARIES

3.1. General Conventions

Unless otherwise stated, summary statistics including the number of subjects (n), mean, standard deviation, median, minimum and maximum will be presented for continuous variables.

Generally, the minimum and maximum values will be presented to the same decimal precision as the raw values, the mean and median values to one more, and the standard deviation, to two more decimal places than the raw values. This decimal place convention may be followed for all data elements. For categorical variables, per category, the absolute counts (n) and percentages (%) of subjects with data, and if appropriate, the number of subjects with missing data, will be presented. Percentages will be presented to one decimal place.

For AEs, medical history and concomitant medications reported on a per-subject basis, the denominator for the percentage calculation will be the number of subjects at risk in each treatment group. A subject will be considered at risk if the subject is in the analysis set and in the subgroup of interest.

All p-values will be rounded to 4 decimal places. If a p-value is less than 0.0001 it will be displayed as “< 0.0001”.

Unless otherwise specified all summaries will be performed by treatment group, all efficacy analyses will be based upon the full analysis population, all safety as well as demographic and baseline characteristic analyses will be based upon the safety population and all PK analyses will be based upon the PK population.

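### The planned safety summaries would usually show an extreme blood pressure or liver value, but not how many subjects per arm had large rises, nor whether transaminase and bilirubin rose in the same subject

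*SAP*

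**What the plan says.** SAP 3.6.2.1 defines the cardiovascular and hepatic AESIs by MedDRA preferred terms. The cardiovascular list includes hypertension and several increased blood pressure terms. The hepatic list begins "PTs of Alanine aminotransferase increased, Aspartate aminotransferase increased, Bilirubin increase". These are reported events, not measured values. Under Protocol 11.1.2 a measurement becomes an adverse event through this route: "Any abnormal assessment or laboratory findings considered by the Investigator to be clinically significant".

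The measurements themselves are handled as follows.

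- **Vital signs (SAP 3.6.4.1):** "The observed data at baseline and change from baseline for each measurement day will be summarized with descriptive statistics", and "A plot of average vital sign parameters will be presented over time". Protocol 13.4.4.5 plans the same summary without the plot.
- **Content of a summary (SAP 3.1):** the number of subjects, "mean, standard deviation, median, minimum and maximum will be presented for continuous variables". Protocol 13.4 agrees.
- **Laboratory tests (SAP 3.6.3):** actual values and changes are tabulated for each scheduled visit. There is then a count against the reference range: "Subjects with clinical laboratory values outside of the normal reference range at any post-baseline assessment will be summarized". Shift tables on the normal range complete the plan.
- **QTcF (SAP 3.6.4.3):** four categories of absolute value and two of increase from baseline.

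Neither document sets a blood pressure category, a multiple of the upper limit of normal, or a joint transaminase and bilirubin tabulation. Neither promises a listing of individual vital signs or routine chemistry values.

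**The concern.** Safety of repeat doses is a secondary objective, and Protocol 5.2 describes CGRP as involved in vasodilation. If blocking it harmed a susceptible minority, the question for the safety review would be how many subjects per arm had a large rise.

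A mean and a maximum per visit do not answer that. The normal-range count does give a number of subjects for liver tests, but a value 1.1 times the upper limit and one 10 times the limit fall in the same cell. Visit-level summaries of each analyte cannot show that a high transaminase and a high bilirubin belonged to one person. The AESI tables do count subjects, but for measured abnormalities they depend largely on each investigator's view of clinical significance. The SAP uses graded categories for QTcF but not for these two domains, which it also singles out.

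**Working it through.** The documents give no figure for blood pressure variability or for any safety comparison, so there is no stated safety figure to reproduce. The only document input is 350 subjects per arm (SAP 1.5). That size does reproduce the stated power for the primary endpoint: 1/(4 × √(2/350)) = 3.307, and Φ(3.307 − 1.96) = 0.911 against at least 90%. Everything below on blood pressure is illustration.

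**Assumptions.** A fraction f = 0.05 of one arm has an added systolic rise of r = 25 mm Hg and the rest have none. Changes are normal with SD 10, 12 or 14. Each subject contributes one reading.

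**Mean.** Difference = f × r = 0.05 × 25 = 1.25 mm Hg. The variance in the affected arm is SD² + f(1 − f)r² = SD² + 29.69, so SE = √[(2SD² + 29.69)/350]. Chance of detection = Φ(1.25/SE − 1.96).

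**Proportion rising 25 or more.** Placebo p0 = 1 − Φ(25/SD). Affected arm p1 = 0.95 × p0 + 0.05 × 0.5. The chance of detection uses the usual two-proportion normal approximation.

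| SD | SE of mean difference | 95% half-width | Detected by mean | p0 | p1 | Detected by proportion |
|---|---|---|---|---|---|---|
| 10 | 0.81 | 1.6 | 34% | 0.6% | 3.1% | 68% |
| 12 | 0.95 | 1.9 | 26% | 1.9% | 4.3% | 46% |
| 14 | 1.10 | 2.2 | 21% | 3.7% | 6.0% | 30% |

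**Does the planned maximum show the problem?** Simulating the same scenario 4,000 times, the median largest change goes from 29 to 42 mm Hg at SD 10, from 35 to 46 at SD 12 and from 40 to 50 at SD 14. The affected arm has the larger maximum in 98%, 94% and 88% of runs, where chance alone gives 50%. So the extreme usually shows.

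**Does the maximum show how many?** Take SD 10 and 350 subjects. With ten subjects raised by 30 mm Hg, or with one subject raised by 45, the median maximum is about 45 in both cases. The expected count at or above 30 differs: 10 × 0.5 + 340 × 0.00135 = 5.5 in the first, and 0.933 + 349 × 0.00135 = 1.4 in the second. The maximum cannot separate one outlier from a cluster; a count can.

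**What a worst-value table would do.** The schedule gives nine post-baseline readings: Day 0 post-dose, Weeks 4 and 8, Week 12 pre- and post-dose, and Weeks 16, 20, 24 and 32. With the shift present at all nine, and within-subject correlation of 0 to 0.7 (assumed), the share of placebo subjects whose worst change reaches 25 mm Hg is about 3–5%, 8–16% and 14–29% at SD 10, 12 and 14. The chance of detection at that single cut is about 65–66%, 31–38% and 17–23%. At SD 14 this is no better than the mean. Higher cuts carry a lower background rate, so several graded cuts are needed.

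**Liver tests.** The documents supply no variability or rates, so no size is computed. The gap follows from the table definitions set out above.

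**The case against.** A reader might infer that blood pressure is analysed only as mean change, that liver tests are analysed only as in or out of range, and that a minority with large rises would go unseen. The documents do not support this. SD, median, minimum and maximum are standard output, laboratory values and changes are tabulated by visit, and every subject with an out-of-range laboratory value is counted. In the illustration the maximum usually gives the affected arm away.

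Nor does event capture rest on a single judgement. Protocol 11.1.2 also counts new undesirable experiences and worsening conditions as adverse events. Its notion of clinical significance covers findings that need treatment or a change in management. Protocol 10.2.11.3 requires review of every laboratory report. AESIs are tabulated by severity, seriousness and discontinuation, and a data monitoring committee reviews safety.

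It can also be said that categories for QTcF create no duty to categorise anything else, that Protocol 5.4 reports no toxicity specific to CGRP blockade to date, that safety is descriptive so detection rates are an imperfect yardstick, and that the tables could be produced later from the same data.

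All of this is fair, and it limits the point to a matter of reporting. It does not supply the missing counts or the joint liver tabulation. Tables added later would have cuts chosen after some sponsor staff are unblinded, which SAP 1.4 places at the last subject's Week 12 visit.

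**Conclusion.** The point holds as a cheap improvement to descriptive safety reporting. The planned outputs would usually reveal an extreme value. They would not show how many subjects per arm had large blood pressure rises or marked liver-test elevations, nor whether transaminase and bilirubin elevations coincided in one subject.

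No confirmatory conclusion or error rate is affected. The blood pressure detection figures rest on an assumed SD, subgroup size and rise. The 30–68% for a proportion applies to one reading and overstates what a single 25 mm Hg cut on the worst of nine readings would deliver. The case for the tables is mainly that they give counts, and only secondarily that they are more sensitive.

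A related inconsistency decides which readings would enter the tables. Footnote 8 to the Protocol Section 2 schedule puts post-dose vital signs within 2 hours, while footnote 8 to SAP Table 1 allows 4 hours.

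**What to change.** Add to SAP 3.6.3 and 3.6.4.1, before any unblinding, descriptive tables by arm of each subject's worst post-baseline result over all assessments, including unscheduled ones:

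- systolic and diastolic blood pressure, by value and by change from baseline, each with more than one cut;
- ALT or AST, and bilirubin, in graded multiples of the upper limit of normal;
- concurrent ALT or AST and bilirubin elevation, shown with ALP, and a listing of subjects who meet the joint criterion.

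The sponsor should choose the cuts. They are reporting categories only and set no rule for managing subjects. The 2-hour and 4-hour post-dose vital-signs windows must be reconciled between the two documents.

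The cost is SAP wording and a few tables from measurements already collected. The downside is more descriptive comparisons without multiplicity control, in which some imbalances will arise by chance.
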